4 STUDY DESIGN

4.1 OVERALL DESIGN

This is a multi-site, two-arm, non-blinded randomized controlled non-inferiority trial that includes 6 months of participation from enrollment to final follow-up.

Hypothesis: We hypothesize that the EPP IUD expulsion rate at 6 months postpartum will be lower than the reported expulsion rate for IPP IUDs (24%) and non-inferior at a 6% margin to the expulsion rate for interval postpartum IUDs (previously reported at 3-5%).

4.2 SCIENTIFIC RATIONALE FOR STUDY DESIGN

Traditionally, IUDs are placed at 6-8 weeks postpartum, therefore the standard of care will serve as the control condition. We are using a 6% non-inferiority assuming a 4% expulsions rate in the interval group according to prior research. This difference is presumed to be clinically meaningful.

4.3 END OF STUDY DEFINITION

A participant is considered to have completed the study after she has completed all phases of the study including the last visit at 6 months postpartum or the optional 12-month postpartum phone call.

5 STUDY POPULATION

Postpartum women delivering a baby at one of the 4 study sites are eligible: University of California, San Diego (UCSD); University of New Mexico (UNM); University of Illinois, Chicago (UIC), and the Naval Medical Center, San Diego (NMCS). 404 women will be enrolled between the 4 different study sites. Participants will be screened for eligibility according to the below criteria using a screening checklist. If eligible and interested in participating, a consent form will be signed.

5.1 INCLUSION CRITERIA

In order to be eligible to participate in this study, an individual must meet all of the following criteria:

- 1) Gave birth less than or equal to 10 days ago
- 2) Desires to use an IUD for contraception (either copper or levonorgestrel-containing)
- 3) Willing and able to sign an informed consent
- 4) Willing to comply with the study protocol
- 5) Age greater than or equal to 18 years
- 6) English or Spanish speaking

5.2 EXCLUSION CRITERIA

An individual who meets any of the following criteria will be excluded from participation in this study:

- 1) Uterine anomaly or leiomyomata which would not allow placement of an IUD
- 2) Desire for repeat pregnancy in less than 6 months
- 3) Evidence of intra-uterine infection (chorioamnionitis or postpartum endometritis) treated with antibiotics
- 4) Ruptured uterus at the time of delivery

- 5) Received a postpartum tubal ligation or immediate postpartum IUD or implant at delivery
- 6) Incarcerated women or women with significant cognitive impairment prohibiting consent
- 7) 4th degree perineal laceration at delivery
- 8) Any medical contraindication to IUD per the US CDC Medical Eligibility Criteria
- 9) Any suspicion of new pregnancy

5.3 SCREEN FAILURES

For individuals who do not meet the criteria for participation in this trial (screen failure) due to not meeting eligibility requirements, the reason will be documented. Potential participants who decline participation will be noted and counted as well. No identifying information will be collected from screen failures.

6 STUDY INTERVENTION

6.1 STUDY INTERVENTION

Control: IUD placed 6-8 weeks postpartum (standard of care, interval placement)

Intervention: IUD placed 2-4 weeks postpartum (early postpartum placement, EPP)

6.2 MEASURES TO MINIMIZE BIAS: RANDOMIZATION AND BLINDING

Participants will be randomized to receiving EPP or Interval IUD placement by chance with a computer-generated randomization scheme in alternating blocks of 4 and 6 stratified by IUD type and site. The group assignment will be in opaque sealed envelope that will be opened by the research assistant. The participant will not be blinded to the group assignment.

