8 STUDY ASSESSMENTS AND PROCEDURES

8.1 EFFICACY ASSESSMENTS

a. Admission/Enrollment Procedure

All women in the 4 study health centers are educated about postpartum contraception during antenatal care. All postpartum women who do not receive an IPP IUD or tubal ligation will be asked if they are interested in the IUD for contraception while on the postpartum floor. If they plan to choose an IUD they will be asked for verbal assent to be pre-screened for the study. If a woman gives verbal consent to be pre-screened, a research assistant will administer the Pre-Participation Questionnaire/Eligibility Checklist. Women who meet inclusion criteria, meet no exclusionary criteria, and want to participate, will be formally consented to participate in the study. Signed informed consent forms will be collected. Subjects will be given copies of the consent document and a copy of the "Experimental Subject's Bill of Rights," and a HIPAA Authorization form for medical data to be released for research purposes. Enrolled participants will then be randomized to EPP or Interval PP IUD placement within 10 days of delivery. The Research Assistant (RA) will open the sealed envelope with the appropriate randomization envelope for the assigned participant number to unblind the participant to her assigned group. Participant numbers are assigned sequentially by each site. Participants will then be asked to complete the Baseline questionnaire.

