9.2 SAMPLE SIZE DETERMINATION

We hypothesize that EPP IUD expulsion will be non-inferior to interval insertion. We propose that greater than or equal to a 6% difference in expulsion at 6 months postpartum between the two arms is clinically meaningful (6% non-inferiority margin). Therefore, we estimate that 404 women will be needed [202 in each arm] to achieve an 80% power to detect a difference of 6% in expulsion at 6 months at a significance level of .05 (two-sided alpha), assuming a 15% loss to follow up and that 5% of IUDs would not be placed after randomization (due to patient preference or new medical contraindication or inability to place the IUDs) and assuming a 4% expulsion rate in the interval group. We estimate that enrolling 404 patients allows us to achieve an 80% power to detect a difference of 6% or more between groups with a 1-sided type 1 error of 0.25%.

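### Section 6.2 alternates blocks of 4 and 6 in an open trial, so up to about 28% of assignments could be known before the envelope is opened

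*Combined protocol and SAP*

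**What the plan says.** Section 6.2 allocates women with a "computer-generated randomization scheme in alternating blocks of 4 and 6 stratified by IUD type and site". On concealment it says: "The group assignment will be in opaque sealed envelope that will be opened by the research assistant." It does not say which block size comes first, that the order of sizes is random, or that the sizes are withheld from sites.

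Section 4.1 describes a "two-arm, non-blinded randomized controlled non-inferiority trial", and section 6.2 adds: "The participant will not be blinded to the group assignment."

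Section 8.1(a) says that "a research assistant will administer the Pre-Participation Questionnaire/Eligibility Checklist". After consent, the research assistant opens the envelope. For women who join by telephone after discharge, the research assistant also goes through the consent form. On numbering, the section says: "Participant numbers are assigned sequentially by each site." IUD type is not mentioned at that point.

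On size, section 5 says that "404 women will be enrolled between the 4 different study sites". Section 9.2 splits them 202 per arm, and section 5.1 names two IUD types, copper and levonorgestrel.

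**The concern.** Mixing block sizes protects concealment only if nobody at the site can tell where a block ends. Strict alternation gives that away. Once the first size in a stratum is known or worked out, every later block boundary is known too. In an open trial the earlier assignments are visible, so whenever one arm's quota in the current block is used up, the remaining assignments in that block are certain. An opaque envelope stops early reading of the slip. It does not stop deduction from the slips already opened.

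The role that screens women also opens envelopes. A person who knows the next assignment could approach a particular woman more or less actively, or time her enrolment within the 10 days after delivery. Section 8.1(a) lets undecided women enrol later, so timing can vary. Selection of this kind at entry, if it rests on unmeasured factors, cannot be reliably corrected in the analysis. The attempt in section 8.1(e) to keep the 6-month clinician blinded does not address it.

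Few events are expected, so small shifts count. With 202 women per arm, 20% not evaluable and the 4% rate assumed in section 9.2, the interval arm expects 202 × 0.80 × 0.04 = 6.5 complete expulsions. As an illustration only, two events moved by selective entry would change that arm's risk by 2/162 = 1.2 percentage points, against a 6-point margin.

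**Working it through.** The plan gives no predictability figure, so there is none to reproduce.

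**Inputs.** Blocks of 4 and 6 in alternation, from section 6.2. Allocation 1:1, from section 9.2 (202 per arm). Total 404 women at 4 sites, from section 5. Two IUD types, from section 5.1, which gives 4 × 2 = 8 strata and an average of 404/8 = 50.5 women per stratum. Actual stratum sizes are not stated, so 25, 50 and 100 are used as assumptions.

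**Certain assignments, block boundaries known.** An assignment is certain when one arm's quota in the block is already filled. For a 1:1 permuted block of size 2m, the expected number of certain assignments is 2m/(m+1).

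- Block of 4 (m = 2): 4/3 = 1.33, or 33.3%. By position, the third is certain with probability 1/3 and the fourth always.
- Block of 6 (m = 3): 6/4 = 1.50, or 25.0%. By position, the fourth is certain with probability 0.1, the fifth with 0.4 and the sixth always.
- One cycle of 10: 1.33 + 1.50 = 2.83, or **28.3%**. Over the trial, 0.283 × 404 = about 114 women.

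Enumerating all 6 sequences of a block of 4 and all 20 of a block of 6 gives the same values. A stratum that stops mid-block can fall lower: at 25 women the share is 28.0% if the first block is a 4 and 24.7% if it is a 6.

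**First size unknown, or order random.** These cases were simulated with an observer who knows the possible sizes, sees every assignment in the stratum, and updates the probability of each block state by Bayes' rule. There were 4,000 replicates per setting, and 2,000 for sizes 4, 6 and 8.

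| Scheme | Certain, n = 25 | Certain, n = 50 | Certain, n = 100 | Best guess correct, n = 50 |
|---|---|---|---|---|
| Alternating, first size known (exact) | 24.7-28.0% | 28.3% | 28.3% | 69.3% |
| Alternating, first size inferred | 19.3% | 23.8% | 26.0% | 69.3% |
| Random order of 4 and 6 | 5.7% | 5.6% | 5.5% | 69.0% |
| Random order of 4, 6 and 8 | 2.3% | 2.2% | 2.3% | 67.6% |

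At 50 women per stratum, applied to 404 women, the certain assignments number about 0.238 × 404 = 96 with the first size inferred, 0.056 × 404 = 23 with random 4/6, and 0.022 × 404 = 9 with random 4/6/8.

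The exact best-guess figure for alternating blocks comes from the expected number of correct guesses per block: 2.83 for a block of 4 and 4.10 for a block of 6, so (2.83 + 4.10)/10 = 69.3%.

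**The case against.** Several objections carry weight.

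- **The 28% is an upper figure.** It needs an observer who knows the sizes, the order and the first size, and who tracks the whole stratum. The protocol prints the sizes and the alternation but not the first size. This stands: from the protocol alone, 24% fits better at the average stratum size.
- **The word may be loose.** The sponsor may have meant sizes that vary at random, in which case the share is already about 6%. This is possible, but nothing in the text says so, and strict alternation is the plain meaning.
- **Safeguards exist.** Under section 8.1(a), all postpartum women without an immediate IUD or tubal ligation are to be asked about the IUD, consent comes before the envelope is opened, and randomization must fall within 10 days of delivery. Section 5.3 counts decliners. These limit steering but do not remove it, because a prediction can be made before the approach.
- **General guessability hardly changes.** Someone inclined to steer can act on a good guess, and the best guess is right about 69% of the time now and 68-69% after the change. This stands, and it narrows the benefit to the removal of certainty.

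A reader might infer that one person at each site screens, obtains consent and opens the envelopes. The documents name one role, not one person, and tie that role to consent review only in the telephone route.

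A reader might also infer from the site-wide participant numbers that stratification by IUD type cannot be delivered. Section 6.2 already specifies strata by type and site, and sequential participant numbers can coexist with a separate envelope series for each stratum. What is missing is operational detail.

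**Conclusion.** The concern holds as a weakness in concealment. On the plain reading of section 6.2, up to about 28% of assignments could be certain in advance, or about 19% to 26% if the first block size has to be inferred in strata of 25 to 100 women. The same two sizes in random order would leave about 6%. These figures rest on strict alternation, complete tracking within a stratum, and assumed stratum sizes.

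The documents do not show that any assignment has been or will be predicted, or that enrolment has been steered, and no effect on expulsion risk has been estimated. The case for change is that a real gain in concealment is available at almost no cost.

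**What to change.** In section 6.2, replace the alternating scheme with permuted blocks of randomly varying size in random order. State that sizes and order are held by the statistician and not disclosed to sites, and take the sizes out of the protocol that sites hold. Adding blocks of 8 to the 4s and 6s brings the certain share to about 2%. If enrolment has begun, apply the new list to unopened envelopes and document the procedure used until then. If the order was in fact random all along, correcting the wording and withholding the sizes is enough.

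As a clarification only, state in section 8.1(a) that the research assistant opens the next envelope in the participant's site-by-IUD-type series, so that it matches the stratification in section 6.2.

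The cost is a regenerated list, replacement of unopened envelopes at four sites, and a wording amendment through the sites' IRBs. Sample size, visits and participant burden do not change.

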7 STUDY INTERVENTION DISCONTINUATION AND PARTICIPANT DISCONTINUATION/WITHDRAWAL

7.1 DISCONTINUATION OF STUDY INTERVENTION

If a participant chooses not to move forward with placement of an IUD, she will remain in the study under observation. Remaining study procedures should be completed as indicated by the study protocol. Reasons for choosing another method of contraception will be documented and the participant followed for the study duration of 6-12 months.

7.2 PARTICIPANT DISCONTINUATION/WITHDRAWAL FROM THE STUDY

Participants may withdraw voluntarily from the study at any time. The PI or study team will not withdraw anyone from the study without specific request from the participant. Medical care will be provided by the patient's clinician as standard of care in the case of study withdrawal. Research participants who sign the informed consent form, and are randomized and receive the study intervention, and subsequently withdraw, or are withdrawn or discontinued from the study will not be replaced.

7.3 LOST TO FOLLOW-UP

A participant will be considered lost to follow-up if she fails to return for any scheduled visits and is unable to be contacted by the study site staff.

The following actions must be taken if a participant fails to return to the clinic for a required study visit:

- The sites will attempt to contact the participant and reschedule the missed visit within one week and counsel the participant on the importance of maintaining the assigned visit schedule and ascertain if the participant wishes to and/or should continue in the study.
- Before a participant is deemed lost to follow-up, the investigator or designee will make every effort to regain contact with the participant, including 3 telephone calls or texts. These contact attempts should be documented in the participant's study file.

8 STUDY ASSESSMENTS AND PROCEDURES

8.1 EFFICACY ASSESSMENTS

a. Admission/Enrollment Procedure

All women in the 4 study health centers are educated about postpartum contraception during antenatal care. All postpartum women who do not receive an IPP IUD or tubal ligation will be asked if they are interested in the IUD for contraception while on the postpartum floor. If they plan to choose an IUD they will be asked for verbal assent to be pre-screened for the study. If a woman gives verbal consent to be pre-screened, a research assistant will administer the Pre-Participation Questionnaire/Eligibility Checklist. Women who meet inclusion criteria, meet no exclusionary criteria, and want to participate, will be formally consented to participate in the study. Signed informed consent forms will be collected. Subjects will be given copies of the consent document and a copy of the "Experimental Subject's Bill of Rights," and a HIPAA Authorization form for medical data to be released for research purposes. Enrolled participants will then be randomized to EPP or Interval PP IUD placement within 10 days of delivery. The Research Assistant (RA) will open the sealed envelope with the appropriate randomization envelope for the assigned participant number to unblind the participant to her assigned group. Participant numbers are assigned sequentially by each site. Participants will then be asked to complete the Baseline questionnaire.

For women who believe they want an IUD postpartum but are unsure whether or not they would like to be part of the study, study staff will provide them with our contact information, an informed consent form, a Subject's Bill of Rights, and a HIPAA Authorization form for medical data to be released for research purposes. If they decide they are interested in participating while they are still in the hospital, the RA will go to their postpartum floor within 24 hours and will pre-screen/enroll as outlined above. For interested women who are being discharged from the hospital, staff will ask them to call us to discuss the study. Over the phone, the RA will ask for verbal consent to pre-screen for the study. If a woman gives verbal consent to be pre-screened, the RA will administer the Pre-Participation Questionnaire/Eligibility Checklist. For women who meet inclusion criteria, meet no exclusionary criteria, and want to participate, the RA will review the Informed Consent and HIPAA Authorization forms and then ask the woman to sign the forms and bring the signed copies to their first study visit. The woman will be officially enrolled in the study at that point. The RA will then open the randomization envelope and schedule the first study visit at either 2 weeks or 6 weeks postpartum once the consent is

signed. The RA will administer the Enrollment Survey either over the phone or in person before the first research visit.

b. Two Week Postpartum Visit

All women randomized to EPP will be scheduled to have an IUD placement visit with their designated prenatal care provider **between 14 and 28 days**. Women will be scheduled to see a nurse midwife or physician based on their obstetrical history and prenatal care. IUDs will be placed by the patient's usual prenatal provider or any provider that the patient would normally be referred to for IUD placement. Whether ultrasound guidance is used for placement will be at the discretion of the clinician. Participants will be compensated with a \$20 gift card for their time and participation after completing the IUD Insertion survey. If a patient in the interval group is seen by her provider at 2 weeks postpartum for other reasons an IUD will not be placed at that visit. Providers will be compensated with a \$5 gift card for their time completing a brief questionnaire for every patient seen at 2 weeks who is participating in the study.

c. Six Week Postpartum Visit

All women will be scheduled to have a routine postpartum visit with their designated prenatal care provider **between 42-56 days postpartum** according to the standard of care at the health centers. Women will be scheduled to see a nurse midwife or physician based on their obstetrical history and prenatal care. Women in the interval group will be assessed for IUD placement at this visit per the standard of care at the center. IUDs will be placed by the patient's usual prenatal provider or any provider that the patient would normally be referred to for IUD placement. Whether ultrasound guidance is used for placement will be at the discretion of the clinician. Participants will be compensated with a \$20 gift card for their time and participation. Participants will be asked to complete either the insertion visit questionnaire or the string check questionnaire depending on their assignment group. Providers will be compensated with a \$5 gift card for their time completing a brief questionnaire for every patient seen at six weeks postpartum.

D. Optional String Check Visit:

Whether a follow-up string check visit is scheduled after six weeks will be at the discretion of the clinician according to standard practice of the clinic. String checks are not recommended by the CDC but are common practice. If a string check is scheduled by the clinician at any time (according to their personal practice or participant needs) then the participant will be asked to complete the string check questionnaire at that time.

e. Six Month Follow Up Visit

All women will be scheduled for a 6-month follow up study visit to assess for IUD expulsion, perforation, pregnancy, IUD removals and acceptability. A study clinician will conduct a bimanual pelvic exam, a speculum exam, and a transvaginal ultrasound at this visit. Women will also be asked to complete the 6-month study questionnaire and will be compensated with a \$20 gift card for their time and participation. The clinician will attempt to stay blinded to the participant's group assignment by not reviewing the medical chart prior to the visit.

f. 12 Month Optional Follow Up Call

During baseline survey data collection, all women will be asked if they consent to a 12-month follow up phone call to assess for IUD expulsion, perforation, pregnancy, IUD removals and acceptability.

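### Section 8.1 does not describe how the stratification by IUD type promised in 6.2 is delivered, and the primary comparison in 9.4.2 uses neither stratification factor

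*Combined protocol and SAP*

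**What the plan says.** All references are to the combined protocol and SAP.

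- **Section 6.2** specifies a "computer-generated randomization scheme in alternating blocks of 4 and 6 stratified by IUD type and site". On concealment it adds: "The group assignment will be in opaque sealed envelope that will be opened by the research assistant".
- **Section 8.1(a)** is the working instruction. The research assistant opens the "appropriate randomization envelope for the assigned participant number to unblind the participant to her assigned group. Participant numbers are assigned sequentially by each site". IUD type is not mentioned. The telephone route in the same section also has no step that refers to type.
- **Before allocation**, "a research assistant will administer the Pre-Participation Questionnaire/Eligibility Checklist". The content of that checklist is not in the document. The Baseline questionnaire comes after the envelope is opened.
- **Inclusion criterion 2** (5.1) reads "Desires to use an IUD for contraception (either copper or levonorgestrel-containing)". It sets no time by which a type must be chosen.
- **Section 9.4.2** compares complete expulsion between arms in the modified intention-to-treat cohort with a Wald test, and judges non-inferiority by whether the confidence interval for the risk difference crosses 6%. Neither type nor site appears in that analysis.

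**The concern.** Two device types at four sites make 2 × 4 = 8 strata, so blocked randomisation stratified by both factors needs eight sequences. The only key that 8.1 gives for choosing an envelope is a participant number that runs in order within a site. A site that packed its envelopes from 8.1 alone could reasonably hold one series. A copper user and a levonorgestrel user enrolled one after the other would then take consecutive envelopes from the same block.

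Three things are at stake. Sites could carry out allocation differently, and the trial could report a stratification that some of them did not perform. Balance by device, which the investigators chose to control for an expulsion endpoint, could be left to chance. And the planned primary analysis makes no use of either factor, so any precision that they offer is given up even where the stratification is carried out as 6.2 intends.

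**Working it through.** **1. The two sections side by side.** Section 6.2 names two factors, type and site. Section 8.1 names one, site, through the participant number. It neither states nor rules out separate number ranges or envelope sets per type. So 8.1 is silent on delivery by type. It does not contradict 6.2.

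**2. Imbalance if each site runs one series.** Inputs: 404 women and 4 sites (section 5), blocks of 4 and 6 (6.2). Assumptions, because the document gives neither: 101 women per site and a copper share *p* of 10% to 30%. Blocking holds the arms nearly equal within site, so the between-arm difference in copper users has variance close to 404 × *p*(1 − *p*):

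- *p* = 0.10: √(404 × 0.09) = 6.0
- *p* = 0.20: √(404 × 0.16) = 8.0
- *p* = 0.30: √(404 × 0.21) = 9.2

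Simulation of the block scheme (4,000 trials per scenario) agrees:

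| Copper share | SD, one series per site | Chance of a difference of 10 or more | SD, series by type and site |
|---|---|---|---|
| 10% | 6.1 | 13% | about 2.0 |
| 20% | 8.0 | 23% | about 2.0 |
| 30% | 9.3 | 31% | about 2.0 |

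With series by type and site, the chance of a difference of 10 or more is effectively nil.

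**3. What such an imbalance could do to the endpoint.** First, the evaluable number. Section 9.2 assumes 4% expulsion, a 6% margin and 80% power. With its two-sided 0.05, n = 2 × 0.04 × 0.96 × (1.960 + 0.842)² / 0.06² = 167.4, so 168 per arm. Then 168 × 1.20 = 201.6, which matches the stated 202. Expected expulsions are 168 × 0.04 = 6.7 per arm. The standard error of the risk difference is √(2 × 0.04 × 0.96 / 168) = 0.021, or 2.1 percentage points.

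A difference of 10 copper users is 10/202 = 5.0 points of copper share. If expulsion risk differed between devices by 2 to 10 points (assumed; the document gives no figure), the risk difference would move by 0.050 × 2 = 0.1 to 0.050 × 10 = 0.5 points. That is small against a 2.1-point standard error and a 6-point margin.

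**4. What stratifying the analysis by type would gain.** Let *δ* be the device difference in expulsion risk. The overall per-woman variance is 0.04 × 0.96 = 0.0384, of which *p*(1 − *p*)*δ*² lies between devices and is removed by stratifying. Power is Φ(2.802/√(1 − *r*) − 1.960), where *r* is the share of variance removed.

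- *p* = 0.20, *δ* = 2 points: *r* = 0.16 × 0.0004 / 0.0384 = 0.2%; power 80.0% becomes 80.1%.
- *p* = 0.20, *δ* = 10 points: *r* = 0.16 × 0.01 / 0.0384 = 4.2%; power 80.0% becomes 81.6%.
- *p* = 0.30, *δ* = 10 points: *r* = 0.21 × 0.01 / 0.0384 = 5.5%; power 80.0% becomes 82.2%.

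A separate simulation with assumed device-specific expulsion rates gave the same picture: a gain of 0 to 2 points of power and no loss.

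**The case against.** The strongest reply is that 6.2 is the section that specifies the scheme, and 8.1 is an operating summary that need not repeat it. Numbers assigned in order by a site are compatible with two number ranges per site, one for each device, and the reference to the appropriate envelope may mean exactly that. This stands. A reader might infer that 8.1 cannot deliver the stratification, but the document nowhere says that a site holds only one series.

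A reader might also infer that a woman undecided between devices is eligible yet has no stratum, or that type is first recorded after allocation and could be influenced by the arm. The document supports neither. The wording of criterion 2 most naturally means that both types are allowed, and the checklist completed before randomisation may record the choice. What is missing is a stated rule.

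The reply on consequence also largely stands. Under a single series, assignment is still random and balanced within site. Chance imbalance by device is then not bias, and the confidence interval already covers it. The validity of the unstratified Wald comparison does not depend on stratification by type.

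One part of the reply does not stand: that a stratified analysis is only a separate preference. Where a trial randomises within strata, analysing by those strata follows from the design, and here it costs no power.

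**Conclusion.** The point holds as a gap between 6.2 and 8.1, together with a primary analysis in 9.4.2 that does not use the stratification factors. It does not hold as a demonstrated failure of the randomisation. The cost is promised balance, reproducibility of the allocation procedure across four sites, and a little precision. The trial's validity is not at risk.

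The imbalance of about 6 to 9 women (standard deviation), against about 2, is conditional on one series per site, equal site sizes and a copper share of 10% to 30%. The possible shift of 0.1 to 0.5 points in the risk difference, and the power gain of 0 to 2 points, rest on assumed device differences in expulsion. If the sites already hold separate series per type, the allocation part is settled by stating so, and the analysis part remains.

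**What to change.** 1. In 8.1, on both the in-hospital and telephone routes, require intended IUD type to be recorded on the Eligibility Checklist before the envelope is opened.
2. In 8.1, state that each site holds a separate numbered envelope series for each type, and that the next envelope comes from the series for the recorded type.
3. Keep type as randomised in the dataset as its own variable, distinct from the device placed. A later change of device does not change the stratum.
4. In 9.4.2, estimate the primary risk difference and its confidence interval stratified by randomised type and site, for example by Mantel-Haenszel, and name the variance estimator in advance. With 6 to 7 expulsions expected per arm over eight strata, the method must tolerate strata without events.
5. Leave inclusion criterion 2 unchanged. Requiring a firm choice would needlessly exclude undecided women. An undecided woman can be assigned by her stated leaning at randomisation and analysed in that stratum.

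The cost is a few sentences of protocol text, one checklist field and, where a site holds only one series, re-packing its envelopes. The analysis change needs no extra participants.
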